5.1.7.2 Study treatment compliance

Treatment compliance will be assessed based on eDiary data.

The study treatment compliance with the prescribed study treatment dose regimen will be assessed by the sponsor based on eDiary data. On each day, subjects will be asked to enter in the eDiary the number of capsules taken in the morning and evening. The subjects will receive a reminder alarm (through the device) to take their morning and evening doses of study medication.

For each time interval between two visits (i.e., “period”), the eDiary based study treatment compliance will be calculated by the sponsor using the following formula:

eDiary based study treatment compliance = Total number of times the subject took study treatment at the prescribed dose regimen during the period / Total number of times the study treatment should have been taken at the prescribed dose regimen during the period × 100

The prescribed starting dose corresponds to the dose assigned to the subject by the IRT system at randomization visit. In the event of study treatment adjustment [see Section 5.1.2], the prescribed dose corresponds to the new study treatment dose. The starting date of the new study treatment dose will be the date when the investigator/delegate contacts the subject to provide him/her instructions for study treatment adjustment.

The period is defined as the number of days between visit n (or date of first study treatment intake if randomization visit) and visit n+1 (or date of last study treatment intake if EOT visit).

The number of times the study treatment should have been taken at the prescribed dose regimen in a given period is calculated as follows:

- Number of days in the period × 2

Study treatment interruption(s) will be ignored when calculating the study treatment compliance based on the eDiary.

Between visits, study treatment compliance based on the eDiary is expected to be at least 80%. The sponsor will inform the site staff and CRA about any compliance values below 80%. Compliance values below 80% without a medical justification (e.g., AE) and not related to an eDiary completion issue will be considered as a protocol deviation, which will be reported as such to the sponsor by the CRA. In such cases, the investigator must discuss and clarify the reasons for non-compliance with the subject and take appropriate actions to avoid re-occurrence.

5.1.8 Study treatment dose adjustments and interruptions

Study treatment dose adjustment, other than described in Section 5.1.2 is prohibited.

Study treatment may be temporarily interrupted in response to an AE, or other reasons (e.g., diagnostic or therapeutic procedure, study treatment forgotten).

If study treatment is interrupted by the subject for any reason, he/she must immediately inform the investigator.

Interruptions of study treatment must be kept as short as possible.

All study treatment interruptions of at least 2 consecutive days and/or due to an AE must be recorded in the eCRF.

5.1.9 Premature discontinuation of study treatment

The decision to prematurely discontinue study treatment may be made by the subject, the investigator, or sponsor personnel. The main reason (e.g., AE, lack of efficacy, study terminated by sponsor) must be documented in the eCRF.

A subject has the right to prematurely discontinue study treatment at any time, without any justification, by withdrawing from study treatment only or by withdrawing from any further participation in the study (i.e., premature withdrawal from the study [see Section 8.2]). Although a subject is not obliged to give his/her reason for prematurely withdrawing from the treatment or the study, it is recommended that the investigator makes a reasonable effort to ascertain the reason(s), while fully respecting the subject's rights.

The investigator must discontinue study treatment for a given subject if, on balance, he/she believes that continued administration would be contrary to the best interests of the subject.

Study-specific criteria for discontinuation of study treatment are described in Section 5.1.10.

A subject who prematurely discontinues study treatment is **NOT** considered as withdrawn from the study and will be followed in the PTOp, provided that the subject's consent for this participation in the study has not been withdrawn. Assessments including safety follow-up that are to be performed at each site visit are described in Section 7.1, Table 5 and Table 6.

A subject who prematurely discontinues study treatment and withdraws consent to participate in any further study assessments is considered as withdrawn from the study. Subjects who die or are lost to follow-up are also considered as withdrawn from the study. Withdrawal from the study and follow-up medical care of subjects withdrawn from the study are described in Sections 8.2 and 8.4, respectively.

5.1.10 Study-specific criteria for interruption / premature discontinuation of study treatment

5.1.10.1 Pregnancy

If a subject becomes pregnant while on study treatment, study treatment **must** be permanently discontinued. The investigator/delegate must counsel the subject and discuss the risks of continuing with the pregnancy and the possible effects on the fetus.

5.1.10.2 Cardiovascular event

Subjects **must** be permanently discontinued from study treatment at any time during the study in the event of heart failure leading to in-patient hospitalization or prolongation of ongoing hospitalization.

5.1.10.3 Renal function

Subjects **must** be permanently discontinued from study treatment at any time during the study if eGFR < 15 mL/min/1.73m² or in the event of acute kidney injury Common Terminology Criteria for Adverse Events (CTCAE) grade 2 or above (i.e., creatinine > 2 × baseline creatinine, creatinine > 4.0 mg/dL or 353.6 µmol/L, hospitalization indicated, life-threatening consequences, dialysis indicated) [[CTCAE 2010](#)].

5.1.10.4 Cerebrovascular event

Subjects **must** be permanently discontinued from study treatment at any time during the study in the event of stroke CTCAE grade 3 or above (i.e., severe neurological deficit, life-threatening consequences, urgent intervention indicated) [[CTCAE 2010](#)].

5.2 Previous and concomitant therapy

5.2.1 Definitions

A previous therapy is any treatment for which the end date is prior to the signature of the ICF.

A therapy that is study-concomitant is any treatment that is ongoing or initiated after the signature of the ICF, or initiated up to 30 days after study treatment discontinuation.

A therapy that is study treatment-concomitant is any treatment that is either ongoing at the start of study treatment or is initiated during the study treatment period.

Local or international treatment guidelines [[Biegstraaten 2015](#); [Politei 2016](#); [Schiffmann 2017](#)] for the management of subjects with FD will apply whenever relevant to the study. These guidelines include the use of ERT and adjunctive therapies.

5.2.2 Mandatory concomitant therapy

Mandatory therapy includes any treatments required for contraception purposes in women of childbearing potential.

5.2.3 Allowed concomitant therapy

Treatments considered necessary for the subject's well-being and not categorized as forbidden concomitant medications are allowed during the study and must be documented in the medical charts.

5.2.3.1 *Angiotensin-converting enzyme inhibitor or angiotensin receptor blocker*

Subject must not have initiated ACE inhibitor or ARB therapy within 4 weeks prior to screening. ACE inhibitor or ARB therapy, if used by the subject, must be at a stable dose for at least 4 weeks prior to screening. During the study, initiation or dose adjustment are allowed based on investigator judgment.

5.2.3.2 *Pain medications*

During the study, the use of adjuvant pain medications, non-opioid and opioid analgesics is allowed if judged medically required by the investigator. Initiation or dose adjustment of pain medications should be done as described in Section 5.2.3.2.2.

5.2.3.2.1 *Pain medications used in Fabry disease*

A list of pain medications used in FD is provided in [Table 2](#).

Subject must not have initiated adjuvant pain medications (i.e., anti-epileptics, TCAs and SNRIs/SSRIs) within 4 weeks prior to screening. The dose regimen of adjuvant pain medications used chronically by the subject at screening must be stable for at least 4 weeks prior to screening.

Table 2 List of pain medications used in Fabry disease

Categories	Pain medications
Adjuvant pain medications	
• Anti-epileptics: e.g., carbamazepine, gabapentin, phenytoin, pregabalin, oxcarbazepin, lamotrigine, topiramate;• TCAs: e.g., amitriptyline, nortriptyline;• Other antidepressants (SNRIs/SSRIs): e.g., duloxetine, venlafaxine.
Non-opioid analgesics	
• NSAIDs: e.g., acetylsalicylic acid / aspirin, paracetamol/acetaminophen, ibuprofen, naproxen, diclofenac, metamizole;• Topical analgesics: e.g., lidocaine, prilocaine, capsaicin.
Opioid analgesic	
• “Weak” opioids: e.g., codeine, dihydrocodeine;• “Strong” opioids: e.g., morphine, oxycodone, tramadol, fentanyl, methadone, hydromorphone, mepiridine.

NSAID = non-steroidal anti-inflammatory drug; SNRI = serotonin-norepinephrine re-uptake inhibitor; SSRI = selective serotonin re-uptake inhibitor; TCA = tricyclic antidepressant.

5.2.3.2.2 *Rescue medications for unbearable pain*

In the event of unbearable pain, rescue pain medications may be considered. An IPMP will be provided by the investigator/delegate to each subject with customized instructions regarding the use of pain medications during the study.

The IPMP will list the pain medications ongoing at the screening visit that the subject should continue taking during the study. It will also include a list of new pain medication(s) or dose adjustment that should be made in the event of unbearable pain taking into account the subject’s background pain medication(s) and previous response to pain medication(s). The IPMP will be applicable starting at screening visit and until the EOT visit or the last visit of the PTO (as applicable). The IPMP will also include instructions regarding the need to contact the investigator/delegate. The investigator/delegate and the subject will sign the IPMP at the screening visit and a copy of the IPMP will be given to the subject.

A sample of the IPMP template is provided as [Appendix 1](#).

Depending on the background pain medication(s) of the subject, and provided that the medication is not categorized as forbidden concomitant medication [Section 5.2.4], the rescue pain medication(s) may include one or more of the following options:

- Initiation or dose escalation of adjuvant pain medication(s) (i.e., anti-epileptics, TCAs, SNRIs, SSRIs);
- Initiation or dose escalation of opioid analgesic drugs;

- Initiation or dose escalation of non-opioid analgesics drugs (i.e., non-steroidal anti-inflammatory drugs [NSAIDs], topical analgesics).

The subject will be prescribed the rescue pain medication(s) listed in his/her IPMP. In the event of pain worsening that is not bearable, the subject will be instructed to:

- Apply the IPMP agreed with his/her investigator/delegate at the time of the screening visit;
- Contact his/her investigator/delegate as soon as possible.

The investigator/delegate will advise the subject on pain treatment adjustment in the event of unbearable pain and will document the discussion in the hospital charts.

If, after the modification of pain treatment, the subject still suffers from unbearable pain, the investigator/delegate should discuss alternative therapeutic options with the subject, including the possibility to (re-)initiate ERT treatment (if available at the site).

Details on the pain medications taken for unbearable pain will be collected in the eDiary [see Section 5.2.5.2].

5.2.3.3 *Antidepressants used to treat depression*

Subject must not have initiated antidepressants (i.e., SNRIs, SSRIs, TCAs) within 4 weeks prior to screening. The doses of antidepressants used by the subject at screening must be stable for at least 4 weeks prior to screening.

During the study, initiation or dose adjustment are allowed based on investigator judgment.

5.2.4 **Forbidden concomitant therapy**

5.2.4.1 *Enzyme replacement therapy (agalsidase alfa, agalsidase beta)*

Subjects on ERT with neuropathic pain at screening (“switch”) must agree to stop ERT administration for about 8 months (6–7 weeks screening + 6 months of double-blind treatment). Recently published recommendations by the European Fabry Working Group have defined ERT stopping criteria which include the lack of response for 12 months when the sole “indication” for ERT is neuropathic pain, and the subject’s request to stop ERT [Biegstraaten 2015].

Subjects off ERT with neuropathic pain at screening (“naïve” or “pseudo-naïve”) who are planned for imminent initiation of treatment with ERT are not eligible for enrollment in the study [see Section 4.4], and initiation of ERT will therefore not be withheld for these subjects.

Although discouraged throughout the whole study, subjects may be allowed to (re-)initiate ERT treatment (if available at that site) if judged medically required due to significant FD

progression (e.g., significant renal function deterioration or cardiac function deterioration) based on investigator judgment. In such case, the subject may continue taking the study treatment.

5.2.4.2 *Inhibitors of glucosyl ceramide synthase, α -galactosidase A chaperone, investigational drugs*

To avoid concomitant administration of medications that would either compete with lucerastat as they have a similar mechanism of action or have an uncertain effect on neuropathic pain in subjects with FD, the following concomitant therapies are forbidden from screening visit until the EOT visit or the last visit of the PTO (as applicable):

- Any inhibitor of GCS (e.g., miglustat, eliglustat);
- Any α -GalA chaperone (e.g., migalastat);
- Any other investigational drug (e.g., ibiglustat/venglustat, pegunigalsidase alfa).

If a subject takes any of the forbidden medications listed in Section 5.2.4, the investigator/delegate must contact the sponsor to discuss further follow-up actions including stopping/interrupting study treatment as appropriate.

5.2.5 Reporting of previous / concomitant therapy in the electronic case report form and electronic diary

5.2.5.1 *Fabry disease-specific therapies*

Any previous administration (at any time prior to screening) of ERT (i.e., agalsidase alfa [Replagal[®]], agalsidase beta [Fabrazyme[®]]) will be recorded in the eCRF.

For treatments received in the last 12 months prior to screening, start/end dates of administration, reason for discontinuation and dose regimen if known, will be recorded in the eCRF.

For treatments stopped before the last 12 months prior to screening, start/end dates, dose regimen, and reason for discontinuation if available in the hospital chart will be reported in the eCRF.

In addition, history of ERT infusion reactions including anaphylactic and allergic reactions will be collected in the eCRF.

ERT infusion reactions [Fabrazyme[®] USPI, Replagal[®] SmPC] include:

- Life-threatening anaphylactic and severe allergic reactions;
- Localized angioedema (including swelling of the face, mouth, and throat);
- Bronchospasm;

- Generalized urticaria, rash, pruritus, flushing;
- Dysphagia;
- Hypotension, hypertension;
- Tachycardia, bradycardia;
- Dyspnea, chest discomfort, chest pain, peripheral edema;
- Nasal congestion, throat tightness;
- Nausea, vomiting, abdominal pain, diarrhea;
- Paresthesia, pain in extremity, myalgia;
- Pyrexia, feeling hot or cold, chills, sweating, hives;
- Headache, dizziness/lightheadedness;
- Fatigue, somnolence.

If ERT therapy is (re-)initiated during the course of the study [see Section 5.2.4.1], the date of each ERT infusion, dose and detailed reason for (re-)initiation will be recorded in the eCRF (e.g., treatment-emergent renal or cardiac signs and symptoms fulfilling class I criteria recommendation to initiate ERT [Biegstraaten 2015]).

Other therapies (experimental or not) used to treat FD (e.g., inhibitor of GCS [e.g., miglustat, eliglustat, ibiglustat/venglustat], α -GalA chaperone [e.g., migalastat], or ERT [e.g., pegunigalsidase alfa / PRX-102, moss-aGal]) in the past 12 months will be recorded in the eCRF. For each therapy, the start/end dates, route of administration, and reason for discontinuation will be recorded. In addition, dose and frequency of administration should be recorded if available.

5.2.5.2 *Pain medications*

Previous pain medications [see Section 5.2.3.2 for definitions] if discontinued less than 30 days prior to signing the ICF and pain medication ongoing at the screening visit must be recorded in the eCRF. The generic name, start dates and end dates (if applicable) of administration, route, dose regimen, and indication will be recorded in the eCRF.

Starting at the screening visit, the subject will be asked on a daily basis to record the use of pain medication (e.g., dose regimen, initiation of a new medication) in the eDiary [see Section 7.2.2.1 for more detail on the eDiary] until the EOT visit or the last visit of the PTOP (as applicable).

Pain medications taken by the subject during the FU period after he/she has returned the eDiary will be collected in the eCRF.

5.2.5.3 *Other therapies*

The use of other (i.e., not covered in Sections 5.2.5.1 and 5.2.5.2) study-concomitant therapy (including contraceptives and traditional and alternative medicines, e.g., plant-, animal-, or mineral-based medicines) will be recorded in the eCRF.

Any other previous therapy must be recorded in the eCRF if discontinued less than 30 days prior to signing of the ICF.

The generic name, start/end dates of administration, route, dose regimen, and indication will be recorded in the eCRF.

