4.3 Inclusion criteria

For inclusion in the study, the subject must fulfill all the following inclusion criteria at the specified study visits. It is not permitted to waive any of the criteria for any subject:

Screening visit criteria

1. Signed and dated ICF prior to any study-mandated procedure;
2. Male or female subjects 18 years old and above;

3. FD diagnosis confirmed with local genetic test results (i.e., presence of at least 1 mutation in *GLA*, the gene coding for α -GalA);
4. Fabry-associated neuropathic pain, as defined by the subject, in the last 3 months prior to screening;
5. ERT treatment status:
 - a) Subject never treated with ERT; or
 - b) Subject has not received ERT for at least 6 months prior to screening; or
 - c) Subject treated with ERT at the time of the screening visit, and meeting all of the following criteria at the time of screening:
 - i) ERT administration for the last 12 months;
 - ii) Stable ERT dose regimen during the last 3 months;
 - iii) Subject agrees to stop ERT administration at the screening visit for approximately 8 months (6–7 weeks screening + 6 months of double-blind treatment).
6. A woman of childbearing potential [see definition in Section 4.5.1] is eligible only if the following applies:
 - Negative serum pregnancy test at screening and a negative urine pregnancy test at randomization;
 - Agreement to undertake monthly urine pregnancy tests during the study and up to at least 30 days after study treatment discontinuation;
 - Agreement to follow a highly effective contraception scheme as described in Section 4.5.2 from screening up to at least 30 days after study treatment discontinuation.
7. A fertile male (physiologically capable of conceiving a child according to investigator judgment) who is sexually active with a woman of childbearing potential is eligible only if the following applies:
 - Agreement to use a condom during the treatment period (starting at randomization) and for up to 3 months after study treatment discontinuation; and
 - Agreement not to father a child during this period.

Randomization visit criteria

8. Adequate subject compliance with completion of an eDiary during the screening period;

9. Subjects with moderate or severe neuropathic pain as determined from daily entries of the modified BPI-SF3 score of “neuropathic pain at its worst in the last 24 hours” in the eDiary during the screening period.

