11. Known hypersensitivity to lucerastat or drug of the same chemical class of iminosugars (e.g., miglitol, miglustat, migalastat), or any of their excipients (including lactose);
12. Initiation or treatment at an unstable dose within 4 weeks prior to screening with any of the following medications:
- a) ACE inhibitor and/or ARB;
 - b) Anti-epileptic;
 - c) TCA and/or other antidepressants belonging to SNRI and selective serotonin re-uptake inhibitor (SSRI) classes.
13. Planned or current treatment with another investigational treatment within 3 months prior to screening;
14. Treatment with any inhibitor of GCS (e.g., miglustat, lucerastat, eliglustat, ibiglustat/venglustat) or an α -GalA chaperone (e.g., migalastat) within 6 months prior to screening;

Randomization visit criteria

15. Treatment with ERT (agalsidase alfa, agalsidase beta) during the screening period.
- In addition, the investigator/delegate must verify that the subject does not fulfill the exclusion criteria checked at the screening visit (as applicable).

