## **14.3 Analysis of stratification variable**

In the event of discrepancies between the IRT system and the eCRF, each of the two stratification variables will be summarized (on the mFAS, PPS, and mFAS-GIS populations, by treatment and overall) in categories for both the IRT-assigned value and the value reported in the eCRF. In addition, shift tables of ERT status at screening according to eCRF (table rows) by ERT status at screening according to IRT (table columns) will be prepared for each treatment group and overall, first based on all subjects

and then separately for each sex (according to eCRF). Otherwise, the stratification variables will be summarized only once.

The stratum information recorded in the IRT system will be decoded from the leading digit of the randomization number (DS.DSREFID) as follows:

- 1: Sex = M, ERT at screening = “switch”
- 2: Sex = M, ERT at screening = “pseudo-naïve” / “treatment naïve”
- 3: Sex = F, ERT at screening = “switch”
- 4: Sex = F, ERT at screening = “pseudo-naïve” / “treatment naïve”.

The ERT status at screening according to the eCRF will be determined by checking the medication in the CM dataset where CM.CMCAT = “PREVIOUS FABRY DISEASE SPECIFIC THERAPY” and (CMCLAS=“ENZYMES” or CMDECOD in [“PEGUNIGALSIDASE ALFA”, “MOSS-AGAL”]) and the corresponding end date (CM.CMENDTC [possibly incomplete] vs the screening date [last screening in the event of re-screening]). In the event of missing end date, ERT status will be presumed to be “switch”.

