#### **15.2.4 Sensitivity analyses**

In the event of discrepancies for the stratification factors between the IRT system and the eCRF, the analysis described in Section 15.2.3 will be repeated using the stratification factors as entered in the eCRF and considered as a sensitivity analysis of the main analysis.

The robustness of inferences from the primary endpoint analysis to deviations from its underlying modelling assumptions will be explored using several sensitivity analyses. Table 11 gives an overview of the planned sensitivity analyses that are described in this section.

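### SAP 14.3 presumes switch when the ERT end date is missing, but the protocol tolerates a missing end date for ERT stopped over 12 months before screening, and those subjects are pseudo-naive

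*Protocol*

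**What the plan says.** Randomization is stratified by sex and by ERT status at screening. Two definitions fix the ERT strata. A switch subject meets inclusion criterion 5c: "Subject treated with ERT at the time of the screening visit, and meeting all of the following criteria at the time of screening". A pseudo-naive subject meets 5b: "Subject has not received ERT for at least 6 months prior to screening". Treatment-naive subjects join the pseudo-naive in the non-switch stratum. SAP section 2 uses the same 6-month boundary.

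Protocol 5.2.5.1 sets two standards for recording past ERT in the eCRF. For recent ERT: "For treatments received in the last 12 months prior to screening, start/end dates of administration, reason for discontinuation and dose regimen if known". For ERT that ended earlier: "For treatments stopped before the last 12 months prior to screening, start/end dates, dose regimen, and reason for discontinuation if available" in the hospital chart.

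SAP 14.3 derives eCRF ERT status from the medication record. It sets the end date, which it notes may be incomplete, "vs the screening date [last screening in the event of re-screening", and gives neither a direction nor a window for the comparison. For a missing date it adds: "In the event of missing end date, ERT status will be presumed to be" switch.

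The derived status has two uses. SAP 14.3 calls for stratum summaries and IRT-by-eCRF shift tables when the two sources disagree. SAP 15.2.4 says that, in the same event, the primary analysis "will be repeated using the stratification factors as entered in the eCRF". The analysis sets themselves take stratum information from the IRT system (Protocol 10.1.2, SAP 4.1.2).

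**The concern.** The default and the data-collection rule work against each other. The group for which the protocol openly accepts an absent end date is the group that stopped ERT longest ago, and the SAP resolves that absence by treating the subject as on ERT at screening.

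At stake is how far the stratification checks can be trusted. A long-stopped subject correctly randomized as pseudo-naive would appear in the shift table as an IRT/eCRF mismatch and look like a stratification error. One such mismatch is enough to trigger the sensitivity analysis in SAP 15.2.4. ERT status enters both the imputation model and the ANCOVA there, so that analysis would run on a factor that is wrong for those subjects. SAP 15.2.4 speaks of factors as entered in the eCRF, but ERT status is derived, so the rule in 14.3 decides the value.

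**Working it through.** The plan gives no figure for this classification. The nearest stated figure is the power of the primary test (Protocol 10.5), and it reproduces. With 66 and 33 subjects, a difference of 2 and SD 3, the noncentrality is 2 / (3 × √(1/66 + 1/33)) = 3.127 on 97 degrees of freedom, which gives 87.2% at two-sided 5%. This point does not change it.

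**Step 1: who may lack an end date.** Protocol 5.2.5.1 attaches chart availability to the dates only for ERT that ended more than 12 months before screening. For more recent ERT, the words on knowledge follow the dose regimen and most naturally qualify that item, so dates are expected.

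**Step 2: their true stratum.** More than 12 months off ERT exceeds the 6 months in criterion 5b. These subjects are pseudo-naive.

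**Step 3: what SAP 14.3 returns.** The rule was applied to typical histories under two readings of the unstated comparison. Strict means switch if the end date is on or after screening. The 6-month reading means switch if the end date is less than 6 months before screening. The intervals of 10 and 60 days are assumptions.

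| ERT history | True stratum | Strict | 6-month |
|---|---|---|---|
| No ERT record | non-switch | non-switch | non-switch |
| Stopped 200 or 400 days before screening, date known | non-switch | non-switch | non-switch |
| Stopped over 12 months before, date not in chart | non-switch | **switch (wrong)** | **switch (wrong)** |
| Last ERT on the screening day | switch | switch | switch |
| End date blank, ERT ongoing | switch | switch | switch |
| Last infusion 10 days before screening | switch | **non-switch (wrong)** | switch |
| Re-screened 60 days after stopping | switch | **non-switch (wrong)** | switch |

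Only the undated long-stopped case is wrong under both readings. The last two rows depend on a cut-off that the SAP does not state.

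**Step 4: how many.** The documents give no count of pseudo-naive subjects or missing dates. If 30 subjects are pseudo-naive with earlier ERT and 5–20% have no end date, then 30 × 0.05 = 1.5 and 30 × 0.20 = 6. That is about 2 to 6 subjects, or 2/118 = 1.7% to 6/118 = 5.1%.

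**Step 5: effect on the sensitivity analysis.** This was simulated for 118 subjects (79/39) with SD 3, half of them switch, and an ERT effect on the outcome of 0.5 to 2 points, all assumed except the sample size and SD. Moving 2 to 6 pseudo-naive subjects to switch, independently of arm, leaves mean bias at about 0.00. The treatment estimate shifts by 0.02 to 0.07 points on average in absolute value, against a standard error of about 0.59 that rises to at most 0.60.

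**The case against.** The strongest reply is that a blank end date normally means ongoing treatment, and the SAP reads missing dates that way elsewhere (7.7 for concomitant medication, 14.9 and 14.10 for medical history). That convention does not fit here. Switch subjects stop ERT at the screening visit and their dates are expected, whereas a blank for long-stopped ERT is allowed by design. One presumption cannot serve both.

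A second reply is that the problem is rare. Only a wholly missing date triggers the default. To enrol a subject under 5b the site must also be satisfied that ERT stopped at least 6 months earlier, so having no date at all should be uncommon. That is fair and keeps the point small, though the documents give no rate.

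A third reply is that misclassifying a pre-randomization covariate independently of arm does not bias a randomized ANCOVA. This also stands, and the simulation agrees.

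A reader might go further and infer that switch subjects are misclassified too. Exclusion criterion 15 bars "Treatment with ERT (agalsidase alfa, agalsidase beta) during the screening period", so a compliant switch subject's last ERT falls on or before the screening visit, and a bare date comparison could return non-switch. The documents do not establish this. SAP 14.3 states no operator or window, the 6-month definition in SAP section 2 classifies those subjects correctly, and a stop date equal to the screening visit is a natural entry. For switch subjects the rule is under-specified but not shown to be wrong.

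**Conclusion.** The point holds for one group. Whenever a subject who stopped ERT more than 12 months before screening has no end date, SAP 14.3 assigns switch and the correct stratum is non-switch. This follows from the two texts and does not depend on how the date comparison is read.

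The number affected is unknown and probably small; the range of 2 to 6 rests on assumed counts. The consequence is confined to the IRT-by-eCRF summaries and shift tables and to one sensitivity analysis that runs only if the sources disagree. The main risk is a misleading picture of stratification errors. A materially different treatment estimate is unlikely under the simulated conditions. It would be wrong to infer that the primary or secondary results are compromised, because they use IRT strata. The missing cut-off, incomplete-date rule and re-screening rule in SAP 14.3 are matters for clarification.

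**What to change.** Amend SAP 14.3 in two places.

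1. Remove the default to switch. Query the site about any missing ERT end date before unblinding. Class the subject as non-switch where the eCRF record shows that ERT stopped before the last 12 months, for example through a partial date or a recorded reason for discontinuation. Because switch subjects also stop ERT, the reason should be one other than entering this study. Keep switch only where ERT is recorded as ongoing at screening.

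2. State the 6-month cut-off from SAP section 2: last ERT less than 6 months before screening is switch, otherwise non-switch. Add a rule for incomplete end dates, and say which screening date applies to a switch subject re-screened after stopping ERT.

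Two apparent shortcuts should not be relied on. The documents do not show that the eligibility option met (5a, 5b or 5c) is stored as an eCRF variable, and an undated record cannot by itself show that there was no ERT in the last 12 months.

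The cost is a few sentences in the SAP, a few lines of derivation code and probably a handful of site queries. There are no new assessments and no effect on sample size, power or alpha.
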